1. Securing storage of physical data (e.g., papers) in locked files, and securing storage of digital data (computer files, digital audio) in password-protected files on password protected computers.
2. Making data that may contain identifying features accessible only to members of the research team working under the direction of the investigators during the duration of the project.
3. Use of a study ID on all audio files and transcripts. The transcriptionist do not transcribe any identifying information. Study staff review hard copy transcripts and remove any remaining identifying information (such as names, place names, etc.). All audio files are destroyed after transcription.
4. Ensuring that no data are collected or maintained by investigators which participants do not want to have preserved.
5. Ensuring no participant can be identified in any presentations or publications about this study.
6. All study staff rated current in HIPAA and IRB training.

All drugs and devices used in the research and the purpose of their use, and their regulatory approval status. NA
The source records that will be used to collect data about subjects. Data are collected from the medical record and via patient and provider surveys.

What data will be collected including long-term follow-up. Long-term follow-up is based on data from the medical record collected as part of routine care.

The duration of an individual subject's participation in the study. Physicians were recruited at monthly physician meetings where the study was presented. The first eligible patient visit occurred on 3/31/2016 while the last visit occurred on 6/30/17.

The duration anticipated to enroll all study subjects. Enrollment of physicians began 2/2016 and was completed by 2/2017. Follow-up was assessed through 12/31/2017— 6 months after the final visit. We chose a 6-month follow-up period to balance factors of providing sufficient time for the intervention to make an impact while also reducing loss to follow-up.

a. Data Analysis

Study outcomes

Our primary clinical outcome is the closing of quality care gaps within 6 months of study visits. Individual care gaps are measured at baseline and 6-month follow-up as a total count of any care gap at both time periods. Change in aggregated care gaps from baseline to follow-up is also assessed in four ways: closure of all baseline gaps, closure of any baseline gaps, opening of new care gaps, and presence of no gaps at the end of the study.

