Our primary patient-reported outcomes regarding their care experiences are obtained during post-visit telephone calls using questions drawn from validated survey instruments. Surveys are conducted within 1 week of the eligible primary care visit. We measure outcomes in the domains of patient satisfaction, autonomy, perceived involvement in care, and satisfaction with care.²⁹⁻³⁴ Modeled on the structure of these validated items, we also add several study-specific questions to obtain more detailed information about bringing up top concerns at the beginning of the visit, taking notes and asking questions during the visit, and following up post-visit with friends

and loved ones. Finally, we examine responses to a 5-item PCP survey administered at baseline during study enrollment.

Statistical Methods

We examine baseline characteristics of patients and providers by randomization status using chi-square, t-test, and non-parametric tests as appropriate. For our clinical trial outcomes, we construct generalized linear mixed models (SAS Proc GLIMMIX) with the dichotomized response as a dependent variable (with a logit link), treatment/control arm as a fixed effect and PCP as a random effect to adjust for clustering of patients within PCP. For secondary survey outcomes, the patient reports are dichotomized and analyzed in the same type of mixed models. We also conduct a priori analyses of English vs. Spanish-speaking patients in sub-analyses to determine any differential effects by language. We use SAS version 9.3, SAS Institute, Cary NC.

b. Sharing of Results with Subjects

Results will not be directly shared with patients.

c. Data and/or Specimen Banking

NA

6. Privacy, Confidentiality and Data Security

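### Section 5a designates none of its five care-gap measures as the test of H2, states no alpha or multiplicity rule, and leaves the status of the survey outcomes unclear

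*Combined protocol and SAP*

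**What the plan says.** All of this is in section 5, a. Data Analysis, unless noted.

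- **Clinical outcome (Study outcomes).** "Our primary clinical outcome is the closing of quality care gaps within 6 months of study visits". The next sentence reads: "Individual care gaps are measured at baseline and 6-month follow-up as a total count of any care gap at both time periods". Then: "Change in aggregated care gaps from baseline to follow-up is also assessed in four ways". The ways are "closure of all baseline gaps, closure of any baseline gaps, opening of new care gaps", and having no gaps at the end of the study.
- **Model (Statistical Methods).** The trial outcomes go into a generalized linear mixed model "with the dichotomized response as a dependent variable (with a logit link"), with arm as fixed effect and PCP as random effect. The text does not say which response is meant, and it gives no cut-point or model for the count.
- **Survey outcomes.** Study outcomes says: "Our primary patient-reported outcomes regarding their care experiences are obtained during post-visit telephone calls". It lists four domains and continues: "we also add several study-specific questions to obtain more detailed information". Statistical Methods says: "For secondary survey outcomes, the patient reports are dichotomized and analyzed in the same type of mixed models".
- **Hypotheses (section 1, Objectives, Aim 3).** H1 concerns patient-centered outcomes, H2 a reduction in care gaps, and H3 better collaboration. Section 5a assigns no outcome to H3.
- **Error control.** No alpha, sidedness, power, ranking or multiplicity adjustment for the trial is given anywhere. The sample size of 750 (section 4a) comes with no effect size or power that might show which endpoint was intended.

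**The concern.** A primary outcome has to be one variable with one analysis before its p-value can be read as a test of the hypothesis. Here the primary clinical outcome is a concept with several operational forms, and these can disagree. In a patient with more than one baseline gap, closing any gap and closing all gaps are different events. New gaps are not closure at all. The count nets closed gaps against new ones. As the text stands, each form could be tested unadjusted and each could serve as the H2 result. A reader of the report could not tell whether a favourable gap result was the planned test or one of several.

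The survey labels raise a related question. If the survey measures are primary, H1 is confirmatory and needs its own error control. If they are secondary, it is not.

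Timing makes this harder to settle from the present text. This version is dated 7/12/18, and follow-up ended on 12/31/2017, so the version alone cannot show that a choice preceded the data.

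**Working it through.** The plan states no error rate, so there is no figure to reproduce. The check has four parts.

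**1. Does any reading of the text give one outcome with one model?**

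| Reading | Outcome | Stated model | Result |
|---|---|---|---|
| The count is primary and the rest are only additional | Total count per patient | Logit, dichotomized response | Model does not fit; no cut-point given |
| The aggregated versions are primary | Four binary measures | Fits | Four tests, unranked |
| Individual gaps means each gap type, open or closed | One binary outcome per type | Fits | More tests; the types to be tested are not listed (section 4b introduces its metrics only as examples) |

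No reading gives both a single outcome and a fitting model.

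**2. Size of the error if any one success counted for H2.** Assumptions, none of them from the documents: two-sided 0.05 per test (critical value 1.96), no true effect, and k normal test statistics with equal correlation ρ.

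P(at least one false positive) = 1 − ∫ φ(x) [Φ((1.96 − √ρ x)/√(1−ρ)) − Φ((−1.96 − √ρ x)/√(1−ρ))]^k dx

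| ρ | k = 4 (binary measures) | k = 5 (with the count) |
|---|---|---|
| 0.9 | 9.4% | 10.2% |
| 0.7 | 13.0% | 14.8% |
| 0.5 | 15.6% | 18.3% |
| 0.3 | 17.4% | 20.9% |
| Independent, 1 − 0.95^k | 18.5% | 22.6% |

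One test gives 5%. Counting only false positives in the favourable direction, five measures give 5.1% (ρ = 0.9) to 10.5% (ρ = 0.3), against 2.5% for one test.

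The gap measures are nested, so equal correlation is a simplification. The correlations were therefore also simulated from assumed gap patterns: 1-4 baseline gaps, closure of 20, 40 or 60% per gap, one possible new gap at 10 or 30%, and no clustering. Over 18 scenarios the five-measure rate was 15.7-18.5%, inside the range above.

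**3. What model would the count need?** Under the same assumed patterns, take a patient with n baseline gaps, closure probability q and new-gap probability p:

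- mean = n(1−q) + p
- variance = nq(1−q) + p(1−p)

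The variance/mean ratio is lowest at n = 4, q = 0.2, p = 0.1: 0.73/3.3 = 0.22. It is highest at n = 1, q = 0.6, p = 0.1: 0.33/0.5 = 0.66. A Poisson model assumes a ratio of 1, so its standard errors would be too large by a factor of 1/√0.66 = 1.2 to 1/√0.22 = 2.1. A negative binomial model cannot represent a variance below the mean.

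**4. Thresholds under a fix.** The first Holm step with five measures is 0.05/5 = 0.01. If H1, H2 and H3 are each held at 0.05, the chance of an error in at least one is 1 − 0.95³ = 14.3% if they are independent, and at most 15%.

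**The case against.** - **The plan does name a primary outcome, and the wording suggests the count, since change is assessed in the other ways additionally.** The first half stands: the concept is named, and what is missing is the operational measure. The second half does not settle it, because the only model is for a dichotomized response.
- **The survey labels need not conflict.** The phrases for the clinical and the patient-reported outcomes run in parallel, so primary may mean main within each class. Alternatively, secondary may mean only the added study-specific questions. Both readings are plausible. A reader might infer a flat contradiction; the documents support only an unresolved ambiguity.
- **The error rates need a rule that any one success supports H2, and the plan states no such rule.** This is correct, and the figures are conditional on it. Counting fewer tests also lowers them. With the four binary measures the range is 9.4-17.4%. Leaving out new gaps, which are not closure, the remaining three give 8.4-13.6%. All of these exceed 5%.
- **The choice may have been fixed earlier.** The IRB approved the trial on 1/22/16 (section 4e), before the first visit on 3/31/2016. From the 2018 date a reader might infer that the measure was left open, or chosen, with results in hand. The documents do not support that: they do not say when outcomes were analysed, and the version behind the approval is not among them.

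**Conclusion.** The point holds for the text as it stands, and it should be settled before any gap result is presented as the test of H2. Section 5a designates no gap measure for H2, gives no model that fits the count, and states no alpha or multiplicity rule. This is more than missing detail, because following the text as written means several unadjusted tests of one primary hypothesis.

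The false-positive chance is roughly two to four times that of a single test: 9-17% for the four binary measures and 10-21% for all five. This rests on the assumed 0.05 per test, correlations of 0.9 to 0.3 and an any-success rule. That the rate exceeds 5% does not depend on the exact correlation.

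Confidence is high that this text does not designate a measure. The documents do not show that selective testing took place, or that pre-specification failed. The survey labels are the lesser part: a clarification is needed to know whether H1 is confirmatory.

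**What to change.** In section 5a:

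1. State the alpha and whether tests are one- or two-sided.
2. Name one gap measure as the test of H2, taken from a dated record made before outcome data were seen, and list the others as secondary. The version behind the 1/22/16 approval is the first place to look.
3. If no such record exists, say so. Report every gap measure actually tested for H2 (the five listed, plus any gap types scored separately) with Holm-adjusted p-values across that whole set.
4. If the total count is analysed, use a model suited to a bounded count, adjusted for the baseline count and keeping the PCP clustering. Estimate the dispersion or use robust standard errors. Do not rely on plain Poisson or negative binomial errors.
5. Give the survey outcomes one status. If they are confirmatory and no dated record ranks them, Holm-adjust across all survey items tested, study-specific items included.
6. State which outcomes serve H1 and which serve H3. The only PCP survey described is at baseline, and perceived involvement in care could belong to either hypothesis. State also that error is controlled within each hypothesis and not across the three.

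**Cost.** No new data are needed. If a dated choice is found, most of this is wording; a count model is added only if the count is analysed. Otherwise the report needs a disclosure and adjusted p-values. Some p-values become less favourable (with five measures the smallest must be at or below 0.01 if alpha is 0.05), and H2 may end up with no single confirmatory test.

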1. Protocol

Protocol Title

Aligning the Visit Priorities of Complex Patients and their Primary Care Providers – PCORI 1403-11992

Principal Investigator

[name] MPH

Version Date

7/12/18

Form Author

[name]

Objectives

For **Aim 1** our study objectives were to obtain patient and provider views of their priorities for primary care visits and how to format a PC tablet based tool designed to help complex patients determine their top priorities for their upcoming primary care appointment. In Aim 1, we conducted an iterative series of separate one-on-one interviews with complex patients and their PCPs to characterize the process of prioritization, understand how patients and their providers differ in setting priorities, and create a process for how these differences can be negotiated during time-limited primary care visits.

In **Aim 2** we developed a simple web-based application that can be loaded onto a Tablet PC to be used in the waiting room prior to the visit. This tool was designed to guide patients to define and discuss their top priorities for the visit. IRB approval was not required for this aim as it did not involve human subjects.

In **Aim 3**, we examined the impact of this tool on both patient-centered and clinical care outcomes. We compared complex patients in intervention vs. control arms to test the following hypotheses:

H1: The intervention increases patient satisfaction, autonomy, perceived patient-centeredness, and quality of communication (patient-centered outcomes).

H2: The intervention reduces quality care gaps (clinical outcome).

H3: The intervention improves collaboration (patient/provider outcomes).

2. Background

a. Scientific Background

Patients are Increasingly Complex: The aging of the US population coupled with better disease prevention and treatment efficacy means that more patients are living with multiple comorbidities that require complicated medical regimens.^{1,2} By 2020 there will be an estimated 130 million Americans with one or more chronic conditions.^{3,4} Patients with multiple chronic conditions have more outpatient visits per year, are often prescribed up to 20 medications, generate more health care costs, have more adverse events, and have lower health-related quality of life.⁵ For this proposal, we define “**complex patients**” as patients with two or more chronic conditions who are not receiving the full potential benefit of health

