not meeting one or more evidence-based primary care management outcomes related to preventive screening [e.g. cancer screening], disease management [i.e. risk factor testing or control], or medication taking [evidence of non-adherence based on pharmacy dispensing or self-report]). In these Step 1 interviews, we focus on understanding whether and how patients prepare for upcoming visits and how they conceptualize the relative importance of different health issues. For each participant, we also elicit a specific list of their current health care priorities that they want to discuss with their physician. With each patient's prior consent, in Step 2 we interview each participant's physician. In the Step 2 interviews we elicit the physician's priorities for the patient, compare the physician and patient listed priorities, and investigate how each physician would seek to balance any differences between the two sets of priorities. Finally, in Step 3 we close the loop by returning to the patient. In the Step 3 interviews, we present patients with physician priorities and investigate how the patient perceives any differences between his/her priorities and PCPs.

Aim 2 is the IT development of the tablet application and does not involve human subjects.

Aim 3 Clinical Trial

We conducted a 2-arm parallel group clinical trial with random, concealed allocation at the level of PCP. Both PCPs and patients provided informed written consent. Patients, providers, and waiting room research assistants cannot be blinded to randomization status because treatment patients are given the Visit Planner tool in the waiting room while control patients are not. However, collection of post-visit survey data and assembly of analytic datasets is masked to randomization status. For **Aim 3**, we enroll PCPs and their patients from KPNC primary care practices in Oakland and San Francisco. PCPs are recruited via their weekly practice meetings and through individual in-person contacts.

Intervention

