Intervention patients are provided the Visit Planner on a tablet tool in the waiting room. The tool starts off with a video that explained the purpose of the application and educated patients about the importance of bringing up their concerns early rather than later in the visit. Then, the tool prompts them to choose their top 1 or 2 concerns for the visit from 6 categories (New Problem, Medicines, Need something from the doctor, Old Problem, Stress at home or at work, A personal concern or other). Within each category, patients have the option of choosing 3-4 sub-categories and of inputting additional comments in a free-text field. After identifying their top visit priorities, patients are then prompted to identify how they would use their time during or after the visit to stay involved with their care (e.g., Take notes during the visit, Ask my doctor questions during the visit, Review with a friend or loved one, Check online patient portal after the visit). All patient responses are subsequently printed out as a Visit Planner Summary for the patient to bring into their visit.

Control

Control patients are also met in the waiting room before eligible visits. Control patients are given a 1-page healthy lifestyle education handout.

Patients in both study arms otherwise receive usual care throughout the clinical trial period.

4. Study Population

a. Number of Subjects

Aim 3 clinical trial = 750 patients (modified)

b. Inclusion and Exclusion Criteria

PCP Eligibility: Providers are eligible for inclusion if they have at least 5 potentially study-eligible patients within their patient panel and plan to remain at their current practice for the following year.

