- 3) We obtain verbal informed consent during this phone call to administer a brief patient baseline questionnaire and arrange with patients to meet ahead of time at their primary care practice on the day of their next scheduled visit. For visits that occur > 1 week after the initial phone enrollment, we also make a reminder phone call. Our team has previously created an informatics tool that alerts us when study participants have scheduled an appointment with their primary care physician.
- 4) At the primary care practice prior to their visit, the research assistant obtains written informed consent. Patients allocated to the intervention arm are then given the pre-loaded iPad with the Visit Planner Waiting Room Tool that helps them prepare for their visit. This tool takes approximately 4 minutes to complete. On completion of the program, the research assistant prints out the patient’s answers and the patient can bring this page into the exam room to remind themselves of their visit priorities and plans. As is clearly explained to the patient, none of the answers entered by the patient become part of the medical record and are only for the patient’s own use. Control patients receive the “Healthy Living/Physical Activity - Every Move Matters” KP-designed 2-page pamphlet.
- 5) Patients are called within 2 days after their visit at a previously arranged time and asked to complete the post-visit survey. All patients completing these surveys receive a \$20 gift card mailed to their home.

f. Informed Consent Process

The study investigator or project manager reviews and presents the consent form before the scheduled interview in the waiting room. We ask if the individual has any questions, provide answers, and obtain signed informed consent prior to the interview beginning.

We do not enroll participants if they cannot provide informed consent due to severe cognitive impairment, language issues, or other incapacity. We screen for these issues during the recruitment telephone call. However, any issues of this nature not evident during that call and noted during the consenting process are handled on a case by case basis by the person obtaining informed consent.

Waiver of Informed Consent

N/A

Waiver of Signed Informed Consent

N/A

Alteration of Informed Consent

N/A

Non-English-Speaking Subjects

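### The main H1 survey models adjust for nothing but PCP clustering, so chance differences in interview language between arms stay in the arm estimate and some power is given up

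*Combined protocol and SAP*

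**What the plan says.** Under Objectives, H1 covers patient satisfaction, autonomy, perceived patient-centeredness and quality of communication. Section 5a (Statistical Methods) specifies logit mixed models with "treatment/control arm as a fixed effect and PCP as a random effect to adjust for clustering of patients within PCP". It then extends them to the patient surveys: "For secondary survey outcomes, the patient reports are dichotomized and analyzed in the same type of mixed models". No patient-level covariate is named.

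Language appears in section 5a only as "a priori analyses of English vs. Spanish-speaking patients", run as sub-analyses to look for differential effects. Baseline characteristics are compared between arms with tests, but no rule says what follows if they differ.

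Section 3 gives the design: "We conducted a 2-arm parallel group clinical trial with random, concealed allocation at the level of PCP". No stratification or balancing by language is described. Section 4e, step 3, records that a phone call before the visit is used to "administer a brief patient baseline questionnaire". The content of that questionnaire is not given, and section 5a does not assign it a role in the outcome models.

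**The concern.** Arm varies only between PCPs. A PCP random intercept carries differences between PCPs into the standard error of the arm effect, but it does not take a difference in language mix out of the estimate. Two things would have to be true for this to matter: Spanish-speaking patients are concentrated among some PCPs, and language is related to how patients rate their care. Both are plausible; the documents document neither. The sponsor evidently thinks language may matter, since it planned to look for different effects by language.

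If both hold, the H1 comparison in a given randomization is shifted by chance imbalance in a variable the trial already records, and the test of H1 has less power than it could have. With no adjustment rule, an imbalance found in the baseline table would either be ignored or be handled by a choice made after the fact.

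**Working it through.** **The plan's own figure.** Section 4a gives only "Aim 3 clinical trial = 750 patients (modified". No alpha, power, effect size, response rate, ICC or number of PCPs is stated, so 750 cannot be reproduced. The only cluster-size information in the eligibility criteria (section 4b) is that a PCP needs "at least 5 potentially study-eligible patients within their patient panel". Apart from N = 750, every input below is an assumption.

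**Step 1. Size of the chance imbalance (risk-difference scale).** Assumed inputs:
- K = 50, 75 or 150 PCPs, so m = 750/K = 15, 10 or 5 patients each
- Spanish share s = 10%, 20% or 30%
- ICC of language within PCP, L = 0.1, 0.3 or 0.5
- difference in favourable response between language groups, d = 5, 10 or 20 points
- overall favourable response p = 60%; outcome ICC within PCP, net of language, 0.02

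Formulas:
- SD of the arm difference in Spanish share = sqrt(4·s(1−s)·[1+(m−1)L]/N)
- SD of the resulting shift in the arm contrast = d × that SD
- Variance with language in the model = 4·[p(1−p) − d²s(1−s)]·[1+(m−1)·0.02]/N
- Variance without it = the line above + (SD of shift)²

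Middle case (K = 75, s = 0.2, L = 0.3, d = 0.10):
- SD of imbalance = sqrt(0.64 × 3.7/750) = 0.056
- SD of shift = 0.10 × 5.6 = 0.56 points
- Variance with language = 4 × 0.2384 × 1.18/750 = 0.00150, an SE of 3.87 points
- SE without language = sqrt(3.87² + 0.56²) = 3.91 points
- Share of variance due to language = 0.56²/3.91² = 2.1%
- An effect with 80% power unadjusted has 81% adjusted

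Across the 81 combinations:

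| Quantity | Smallest | Largest |
|---|---|---|
| SD of difference in Spanish share (points) | 2.6 | 9.5 |
| SD of shift in arm contrast (points) | 0.1 | 1.9 |
| SE of unadjusted contrast (points) | 3.7 | 4.4 |
| Variance share due to language | 0.1% | 18.5% |
| Power after adjustment, from 80% | 80% | 87% |

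The share is below 5% in 63 of the 81. Of the 18 above 5%, 17 need d = 20 points. The maximum is at 50 PCPs, 30% Spanish, L = 0.5, d = 20 points.

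**Step 2. A concrete bad draw.** Assume 50 PCPs with 15 patients each, outcome ICC 0.03, 10 PCPs with 70% Spanish-speaking patients and 40 with 7.5%, and 60% favourable response in English speakers.
- Chance that 7 or more of the 10 fall in one arm: 2·P(X ≥ 7), X hypergeometric(50, 10, 25), = 0.289
- A 7:3 split gives a difference in Spanish share of (7−3)/25 × (0.70−0.075) = 0.10
- Language odds ratio 2: 60% becomes 75%, so the shift is 0.10 × 15 = 1.5 points
- Language odds ratio 3: 60% becomes 81.8%, so the shift is 0.10 × 21.8 = 2.2 points
- SE of the arm contrast is about sqrt(4 × 0.235 × 1.42/750) = 4.2 points, so these shifts are about 0.35 to 0.5 of one SE

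**Step 3. The planned logit model.** Simulation of the random-intercept logit model: 75 PCPs × 10 patients, 20% Spanish, L = 0.3, PCP SD 0.25 on the logit scale, true arm log OR 0.5, 400 runs per scenario (Monte Carlo error about 2 points on each power). The baseline score is hypothetical.

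| True language log OR | True score log OR per SD | Adjusted for | Power, arm only → adjusted |
|---|---|---|---|
| 0.5 | 0 | language and score | 81% → 82% |
| 1.0 | 0 | language and score | 78% → 82% |
| 1.0 | 0.5 | language and score | 78% → 82% |
| 1.0 | 1.0 | language and score | 69% → 78% |

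In the second row only language is prognostic, and the empirical SD of the arm log OR hardly moves (0.179 to 0.176). In the last row the average SE rises from 0.168 to 0.184, while the average estimate moves from 0.41 to 0.50. The gain is therefore in power, and the standard error need not fall.

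With a language log OR of 1.0, the arm imbalance in language correlates 0.21 to 0.30 with the unadjusted estimate and about 0 with the adjusted one. With no true arm effect, the unadjusted estimate averages about 0 and rejects in 4% to 7% of runs.

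**The case against.** The strongest reply is that nothing here is an error. Allocation is random and concealed, the PCP random effect puts the differences between PCPs into the standard error, and the simulated test is close to its nominal level. An unadjusted cluster model is a legitimate choice. That stands, and it limits the point to efficiency and to imbalance in the particular draw.

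A second reply is that language is already covered by the sub-analyses, whose within-language contrasts are free of language-mix imbalance, and that the baseline table would reveal an imbalance. This stands in part. The sub-analyses do not give the all-patient estimate, and the baseline tests lead to no stated action.

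Three stronger readings are tempting, and the documents do not support them:
- **That the arm estimate is biased.** Under random allocation the imbalance is due to chance. The documents do not say whether patients were recruited before or after their PCP was allocated, so selective recruitment can be neither shown nor excluded.
- **That the reported intervals are wider than they need be.** The plan analyses odds ratios, and there adjustment need not narrow the interval (step 3).
- **That a useful baseline measure is being discarded.** The questionnaire is described only as brief. No item matching an H1 domain is documented, many H1 items concern the visit itself, and the call is not placed before allocation.

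**Conclusion.** The point holds as a modest, inexpensive improvement. The all-patient H1 models leave out a recorded variable that the sponsor itself regards as a possible effect modifier, and chance differences in it remain in the arm estimate. The likely cost is small: mostly under 5% of the variance of the contrast, and at most 18.5% in the assumed range. The upper end needs strong clustering of language by PCP, a large Spanish-speaking share and a 20-point difference in response between language groups. If language is only weakly related to the ratings, the cost is negligible.

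The point applies whether these outcomes are treated as secondary, as in Statistical Methods, or as primary patient-reported outcomes, as under Study outcomes. It does not extend to the care-gap models or to the test of differential effect by language.

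**What to change.** In section 5a, for each H1 survey outcome, specify arm and interview language (English/Spanish) as fixed effects and PCP as a random effect. Keep language in the model whatever its significance, and report the arm-only model beside it. Add a baseline-questionnaire item only if one exists in the same domain and its answer could not have been affected by knowledge of the PCP's allocation.

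Timing decides the status of this model. The protocol is dated 7/12/18, after the last visit (6/30/17) and the end of follow-up (12/31/2017), and the Objectives describe Aim 3 in the past tense. The change can apply to the main model only if arm comparisons have not yet been examined. If they have, keep the stated model as main and report the language-adjusted model as a labelled sensitivity analysis.

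The cost is a short addition to section 5a and one extra model term, with no new data. The small downside is that the odds ratio becomes conditional on language, which is why both results should be shown.
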